Preemptive Local Analgesia
with Liposomal Bupivacaine in
Vaginal Hysterectomy: A
Randomized Controlled Study

NCT03907033

September 27, 2019

Preemptive local analgesia with liposomal bupivacaine in vaginal hysterectomy: A randomized, blinded, controlled study

[name]

Principal Investigator

April 25, 2018

REVISED: November 27, 2018

May 2, 2019

September 27, 2019

[name], DO

[name]

[name]

Gynecology

[name]

[name]

Anesthesiology

INTRODUCTION

Reduction in immediate postsurgical pain is important as it results in less opioid requirements and fewer opioid-related adverse events such as central nervous system and respiratory depression, nausea, vomiting, ileus, and pruritus. Decreased postoperative pain may also result in shorter recovery room and hospital stays, and higher patient satisfaction.

Preemptive analgesia in form of uterosacral ligament injection has been shown to be effective for patients undergoing vaginal hysterectomy. Injection of bupivacaine into the uterosacral ligaments has been associated with significantly reduced pain scores in the first three hours after surgery as well as lower total narcotic use within the first 24 hours following surgery (1). Preemptive analgesia with bupivacaine during vaginal hysterectomy is standard practice at our institution as part of a multi-modal pain management platform.

Liposomal bupivacaine is a novel formation of local bupivacaine designed to provide prolonged postsurgical analgesia. The drug is encapsulated in multivesicular liposomes, thereby allowing prolonged drug release for up to 72 hours. Its safety and side effect profile is similar to bupivacaine HCl and normal saline (2). In 2011, the FDA approved of its use for single-dose local administration into surgical sites.

The efficacy of liposomal bupivacaine has been demonstrated in orthopedic procedures, hernia repairs, hemorrhoidectomy, and breast augmentation. When compared to bupivacaine HCl, studies suggest liposomal bupivacaine may be more efficacious in terms of lower pain scores, longer time to first rescue opioid dose, decreased total opioid consumption postoperatively, and shorter length of hospital stays (3).

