We plan to enroll women 18-85 years old who will be undergoing outpatient vaginal hysterectomy with or without concurrent prolapse repair surgeries at the Mayo Clinic Hospital in Arizona. Participants will be recruited during the preoperative visit and consented with a written form.

Exclusion criteria will include:

- Known history of hepatic disease evidenced by AST or ALT greater than normal values
- Known history of renal disease evidenced by serum Cr greater than normal values
- Known history of prolonged QT ($QT_c >$ than 500 m/s)
- Opiate tolerance noted by daily use of greater than 20 mg morphine daily oral equivalents per day for minimum one month prior to surgery
- Allergy or contraindication to amide local anesthetics, celecoxib, ketorolac, NSAIDS, acetaminophen, gabapentin, sulfa drugs, or ondansetron. Patients allergic to both oxycodone and hydromorphone

- Patients with acute GI bleed in < 6 months of study
- Adults lacking capacity to consent

MATERIALS AND METHODS

Randomization and Blinding:

Redcap software will generate a randomization list in one-to-one ratio to assign patients to either the study group (receiving both liposomal bupivacaine and bupivacaine HCl) or control group (receiving bupivacaine only). All subjects will be recruited and assigned according to their priority at admission. The pharmacist will use this randomization list and dispense the medication sequentially. Patients, care team in recovery, study team members collecting and recording data, and statisticians will be blinded to randomization assignment. The surgical team and pharmacy will be un-blinded. All patients will be documented in EMR as receiving liposomal bupivacaine to ensure the blind is maintained and to ensure that safety features in the EMR for all patients receiving liposomal bupivacaine are activated.

TREATMENT GROUPS

Patients in both groups will be given a total volume of 40ml and dose of 100 mg plain bupivacaine:

- Patients in the study group will receive a mixture of 0.5% bupivacaine HCl and liposomal bupivacaine in 1:1 ratio. 10cc of the mixture will be injected bilaterally into each uterosacral ligament prior to the colpotomy incision. After entry into the posterior cul-de-sac, an additional 10cc will be injected bilaterally into the deeper uterosacral ligaments (diagram attached as appendix 3).

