Statistical summary descriptives such as mean, median, standard deviation, first quartile, third quartile and range for quantitative data, and frequency and proportions for categorical data will be provided. The objectives of the study comprise the group comparisons between combination liposomal bupivacaine/bupivacaine HCl vs. bupivacaine HCl only for total opioid use in morphine equivalents, total non-opioid use, VAS pain scores, episodes of emesis, total antiemetic use, and patient satisfaction. The normality assumptions will be checked and the appropriate parametric tests such as the two independent sample t-test or non-parametric tests such as the Wilcoxon rank sum test will be used. Group associations with categorical variables will be tested using the Chi-square or Fishers' exact test. The significance level is at 0.05.

SAFETY MONITORING

All patients will be continuously monitored for local anesthetic toxicity or other reaction to liposomal bupivacaine for the entire surgical scope of care. During surgery standard ASA monitors will be in place and in recovery vital signs every 15 minutes with continuous telemetry and pulse ox, with a minimum 2:1 RN monitoring. They will remain in recovery a minimum of 4 hours post op. Continuous surveillance for medication reaction or local anesthetic toxicity including but not limited to tinnitus, perioral numbness, mental status changes, cardiac arrhythmia, respiratory compromise, rash, or hives. 20% intralipid for treatment of toxicity will be available at all times. Patients will also be discharged with specific education regarding signs and symptoms for local anesthetic toxicity and instructions to call the on call physician with mild symptoms and present to the ED if moderate or severe symptoms.

ADVERSE EVENTS

The investigator/study team will report to the Mayo IRB any UPIRTSOs and NonUPIRTSOs according to the Mayo IRB Policy and Procedures.

An adverse event is defined as an untoward or undesirable experience associated with the use of a medical product (i.e. drug, device, biologic) in a patient or research subject. All adverse events that are considered related to the direct use of liposomal bupivacaine will be defined, collected, and reported.

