The principal investigator will be responsible for determining whether an event is related to the direct use of liposomal bupivacaine. An AE will be considered unexpected if the nature, severity, or frequency of the event is not consistent with the risk information previously described for the standard of care procedure or in the package insert for liposomal bupivacaine.

All study-related AEs will be followed until stabilization or resolution.

ADVERSE EVENT REPORTING PERIOD

For this study, the study treatment follow-up period is defined as 7-10 days after the procedure when they are contacted by the study team.

MEDICAL MONITORING

It is the responsibility of the Principal Investigator to oversee the safety of the study at his/her site. This safety monitoring will include careful assessment and appropriate reporting of adverse events as noted above, as well as the construction and implementation of a site data and safety-monitoring plan. Medical monitoring will include a regular assessment of the number and type of serious adverse events.

FUNDING

Pacira Pharmaceuticals, Inc. is funding the study. Pacira Pharmaceuticals, Inc. will pay the institution to cover costs related to running the study; however, they will have no role in randomization, patient care, assessment of data, or development of conclusions. Attempts will be made to publish the results independent of outcome, even for a negative study.

REFERENCES

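### The only general adverse event collection rule visible in the plan is limited to events judged related to liposomal bupivacaine, so other, mainly non-serious postoperative events may go unrecorded in both arms

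*Combined protocol and SAP*

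**What the plan says.** The Adverse Events section of the combined protocol and SAP states: "All adverse events that are considered related to the direct use of liposomal bupivacaine will be defined, collected, and reported". It then assigns the attribution: "The principal investigator will be responsible for determining whether an event is related to the direct use of liposomal bupivacaine". The same section defines an adverse event by its association with use of a medical product. For follow-up to resolution it uses a somewhat wider term, study-related events.

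Two further provisions point to documents that are not reproduced. The study team "will report to the Mayo IRB any UPIRTSOs and NonUPIRTSOs according to the Mayo IRB Policy and Procedures", and the Medical Monitoring section makes the principal investigator responsible for "the construction and implementation of a site data and safety-monitoring plan". Medical Monitoring also provides for regular review of the number and type of serious adverse events, with no limit to related ones.

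On blinding, the Randomization and Blinding section says "The surgical team and pharmacy will be un-blinded". It also says that "study team members collecting and recording data, and statisticians will be blinded to randomization assignment" and "All patients will be documented in EMR as receiving liposomal bupivacaine to ensure the blind is maintained". It does not say to which side the principal investigator belongs.

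The Introduction motivates the trial partly by the prospect of "fewer opioid-related adverse events such as central nervous system and respiratory depression, nausea, vomiting, ileus, and pruritus".

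**The concern.** The rule applies attribution before recording. The usual order is to record every event in both arms and enter attribution as a separate item, so that arms can be compared on what happened and not only on what someone thought caused it. Here the attribution is to a drug that control patients do not receive.

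Two things could follow. First, an event caused by opioids or by the operation itself would not normally be judged related to liposomal bupivacaine, so it could drop out of the record in either arm. That matters somewhat here, because fewer opioid side effects are part of the rationale and patients go home with opioid prescriptions. Second, if whoever judges relatedness knows the allocation, a control event cannot logically qualify, and the rule itself would create a difference between arms.

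What is at stake is the completeness of the safety description. The analgesic-use comparison and the listed secondary outcomes do not depend on this rule.

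**Working it through.** The plan gives no figure on this point to reproduce. The check sets the general rule beside every other safety provision in the visible text and asks what is left over.

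**Covered in both arms without the general rule**
- Allergy and local anesthetic toxicity: assessed on arrival in PACU, before discharge, and by telephone up to day 7-10 (Data Collection).
- Medication reactions during surgery and recovery: an open-ended surveillance list that includes mental status changes, respiratory compromise, rash and hives (Safety Monitoring).
- Nausea, emesis and antiemetic use: PACU doses, then a diary through 72 hours (Data Collection; Appendix I).
- Urinary retention: post void residual above 200 ml (Data Collection).
- Anesthetic and surgical complications during surgery (Appendix I, operative data).
- Unplanned admissions, with the reason (Data Collection).
- Serious adverse events: number and type (Medical Monitoring).

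**The six opioid-related events named in the Introduction**
- Nausea and vomiting: collected by diary.
- CNS depression and respiratory depression: within the recovery surveillance list.
- Pruritus: in recovery it falls under medication reaction as readily as sedation does. At home it has no visible item unless it is reported as an allergic reaction.
- Ileus: visible through the reason for an unplanned admission, and indirectly through the nausea and emesis counts to 72 hours. Without admission it has no visible item of its own.

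**What is left.** Mainly non-serious events after surgery and, above all, after discharge. The diary is described for analgesic use, pain scores, nausea and emesis, and the day 7-10 call for allergy, toxicity and satisfaction. The Appendix I list has no general adverse event item after surgery. For these events the relatedness rule is the only visible one.

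**Does the rule by itself separate the arms?**
- If the person deciding relatedness knows the allocation, no control event can be related to a drug the patient did not receive. The control count under this rule is then zero by construction.
- If that person is blinded, the same test is applied to both arms and nothing in the rule creates a difference. The EMR entry showing liposomal bupivacaine for every patient, together with the blinded data collectors, could support this.
- The documents do not say which case applies.

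**What an all-cause table could show**
- Patients per arm: 104 randomised one-to-one gives 104/2 = 52.
- Exact two-sided 95% upper limit when 0 of 52 patients have an event: 1 - 0.025^(1/52) = 1 - 0.9315 = 0.0685, or 6.8%.
- Power of a two-sided Fisher's exact test at 0.05 with 52 per arm, for event rates assumed here because the plan gives none: 0.208 for 10% against 20%, and 0.068 for 5% against 10%.

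The table would therefore describe the arms and bound rates. It would seldom distinguish them.

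**The case against.** The strongest reply is that absence is being inferred from an incomplete text. The institutional IRB policy and the site safety-monitoring plan are not reproduced. Appendix 2 appears only as a heading, appendix 3 is cited (for the injection diagram) but not shown, and the diary and questionnaire forms are not visible. The sentence does not say that only related events are collected. Other wording hints at wider capture: unexpectedness is judged partly against the known risks of the standard procedure, and deciding whether an event is related presupposes that events reach the principal investigator before attribution. The opioid-event list in the Introduction is background, and neither ileus nor pruritus is a study outcome. The use is described as on-label, and the harms of most interest are already sought in all patients.

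Much of this stands. It rules out treating under-recording as established, and it rules out saying that pruritus goes uncollected, since recovery surveillance covers it. It does not remove the point. The IRB provision concerns reporting, and the content of the monitoring plan is not given, so neither states what is collected. The hints about capture are not a collection rule. No visible sentence supplies a wider rule for non-serious events after discharge.

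A reader might also infer that the rule builds in an excess of events in the study arm. The documents do not support that, because it requires an un-blinded judge and the principal investigator's status is not stated.

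**Conclusion.** The point holds in a limited form. The only general collection rule in the visible text covers events considered related to liposomal bupivacaine. For the remaining, mainly non-serious postoperative events, following it as written may leave no all-cause count by randomised arm.

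The loss is possible rather than established, and its size cannot be calculated, because the plan gives no basis for the share of events that would be called related. A difference between arms created by the rule arises only if relatedness is judged with knowledge of allocation. It would be wrong to infer that control patients go unmonitored, since the targeted provisions apply to both arms. No stated objective and no primary result is affected.

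The conclusion assumes that the documents not shown do not already require all-cause recording. If they do, the remaining defect is that the protocol does not say so. The change is worth making because it is cheap and because events not recorded during follow-up may not be recoverable later.

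**What to change.** Replace the collection sentence in the Adverse Events section with a commitment to record all adverse events in both arms through the day 7-10 contact, regardless of attribution. One open question at the existing PACU, discharge and telephone contacts is enough.

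Record relatedness to the study injection, a term that fits both arms, as a separate field, and state the blinding status of the person who judges it. Where a qualified team member is already blinded, that person could make the judgement.

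Tabulate all events descriptively by randomised arm. Keep patients with unplanned admission in that table: Data Collection excludes their data and counts them as treatment failures without saying whether this extends to safety data. If the site safety-monitoring plan already requires all-cause recording, a sentence saying so would close the collection gap.

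The cost is a wording change, one question at each existing contact, a relatedness entry per event and one more table. The downside is somewhat more recording of routine postoperative complaints, for a table that is descriptive only. No extra visits are needed.

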APPENDIX I

DATA COLLECTION

- I. Demographic data
 - a. Age/date of birth
 - b. BMI
- II. Preoperative data
 - a. Indication for surgery
 - b. Medical history
 - c. Surgical history
- III. Operative data
 - a. Surgery performed
 - b. Operative time
 - c. Pathologic diagnosis
 - d. Total fentanyl dose in mcg during surgery
 - e. Complications during surgery; anesthetic and surgical
- IV. Immediate postoperative data (PACU until discharge)
 - a. Total opioid use in mg morphine IV equivalents
 - b. Antiemetic use as total doses IV antiemetics
 - c. VAS pain scores: cumulative in PACU until discharge
 - d. Urinary retention: determined as post void residual greater than 200 ml on catheterization or bladder scan.

V. Postoperative data to 72 hour (POD 3)

- a. Total opioid use in mg morphine IV equivalents
- b. Non-opioid medication use in total tablets of 600 mg ibuprofen and 500 mg acetaminophen
- c. VAS pain scores: mean of cumulative in PACU until discharge, day of discharge at home, 24 hours (POD 1), 48 hours (POD 2), 72 hours (POD 3). Home VAS scores will be mean of 6 hour intervals each day
- d. Times patients felt nauseated: day of discharge at home, 24 hours (POD 1), 48 hours (POD 2), 72 hours (POD 3).
- e. Episodes of emesis: day of discharge at home, 24 hours (POD 1), 48 hours (POD 2), 72 hours (POD 3).
- f. Antiemetic medication use: day of discharge at home, 24 hours (POD 1), 48 hours (POD 2), 72 hours (POD 3).
- g. Indication for admission (if applicable)
- h. Patient satisfaction with postoperative pain control (0-10; 0=unsatisfied, 10=very satisfied)
 - i. 72 hours
 - ii. 7-10 days post op

ANESTHESIA PROTOCOL

I. Preoperative:

- a. Up to 4 mg Midazolam at providers discretion on transport to OR
- b. Celecoxib 400mg PO (Gyn service order)
 - i. For patients 18-64 years old
- c. Acetaminophen 1000mg PO (Gyn service order)
- d. Decadron 4mg (Gyn service order)
- e. Gabapentin 300-600mg PO (Gyn service order)
 - i. For patients 18-59 years old, order 600mg
 - ii. For patients 60-69 years old, order 300 mg
 - iii. Do not give if >70 years old

II. Intraoperative:

- a. Study group: (OR nurse to retrieve, surgeon to inject)
 - i. Mix 20cc 0.5% bupivacaine HCl and 20 cc liposomal bupivacaine in 1:1 ratio
 - ii. Inject 10cc of mixture into each uterosacral ligament prior to colpotomy
 - iii. After entry into posterior cul-de-sac, inject additional 10cc of mixture into deeper uterosacral ligaments

- iv. Total injection = 40 ml
- b. Control group: (OR nurse to retrieve, surgeon to inject)
 - i. Inject 10cc of 0.25% bupivacaine into each uterosacral ligament prior to colpotomy
 - ii. After entry into posterior cul-de-sac, inject additional 10cc of 0.25% bupivacaine into deeper uterosacral ligaments bilaterally
 - iii. Total injection = 40ml
- c. Anesthesia:
 - i. All patients will receive general endotracheal anesthesia
 - ii. Induction with Fentanyl 1-2 mcg/kg, Propofol/lidocaine, succinylcholine/rocuronium
 - iii. Maintenance with Sevoflurane in air oxygen mixture, and fentanyl prn to a case maximum of 400 mcg, no additional opioids
 - iv. Background propofol infusion (25-75 mcg/kg/min)
 - v. No ketamine
 - vi. Prophylactic antibiotic prior to incision
 - vii. Reversal at provider's discretion with glycopyrrolate/neostigmine, or sugammadex
 - viii. Ketorolac 15mg IV during wound closure
 - ix. Ondansetron 4mg IV during wound closure

III. Recovery:

- a. PACU
 - i. First line: IV Tylenol, PO Oxycodone 5-10 mg or PO hydromorphone 2 - 4 mg mild (VAS 0-4), moderate (5-6), or severe (7-10) pain (Gyn service order)
 - ii. Second line: Fentanyl 25 mcg q 5 min prn to max of 200 mcg for severe pain (7-10) (Gyn service order)
 - iii. Third line: hydromorphone 0.2 mg IV q 5 min to max of 2 mg for severe pain (7-10) refractory to fentanyl (Gyn service order)
 - iv. Ondansetron 4 mg IV PRN up to 2 doses (Gyn service order)
 - v. Promethazine 6.25 mg IV PRN one dose for refractory nausea up to 2 doses (Gyn service order)
 - vi. May give other anti-emetics as needed.
- b. Discharge Medications
 - i. Acetaminophen 1000 (2 OTC 500 mg strength) mg Q8 hrs PRN mild (0-4) to moderate (5-6) pain

- ii. Ibuprofen 600 (prescription 600 mg strength) mg Q8 hours PRN mild (0-4) to moderate (5-6) pain
- iii. Oxycodone 5 or 10 mg Q4 hrs PRN for moderate (5-6) to severe (7-10) pain. Patients will be discharged with two prescriptions: the first to be filled for 10 tablets, the second for additional 20 tablets if needed.
- iv. Hydromorphone 2 or 4 mg Q4 hrs PRN for moderate (5-6) to severe (7-10) pain. Patients will be discharged with two prescriptions: the first to be filled for 10 tablets, the second for additional 20 tablets if needed.
- v. Ondansetron 4 mg PO Q6 hours PRN for nausea
- vi. Prochlorperazine 10 mg PO Q8 hours PRN for nausea

APPENDIX 2

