There are few studies evaluating liposomal bupivacaine in gynecologic surgery. Hutchins et al demonstrated that patients who received transversus abdominis plane (TAP) blocks with liposomal bupivacaine required 50% less total opioid during the first 72 hours following robotic assisted hysterectomy than patients who received bupivacaine (4). While liposomal bupivacaine is promising for management of postoperative pain, it has not yet been studied in vaginal surgery.

The aim of this study is to compare the effects of preemptive analgesia using liposomal bupivacaine mixed with bupivacaine HCl, versus bupivacaine HCl alone for uterosacral ligament injection in patients undergoing vaginal hysterectomy. We hypothesize that the group receiving a combination of liposomal bupivacaine and bupivacaine HCl will report superior postoperative pain management. Enhancement in pain control should confer a decrease in opioid and other analgesic medication requirements, which may contribute to decreased nausea, vomiting, and higher overall patient satisfaction with pain control.

OBJECTIVES

The primary aim of this study is to compare total post-surgical analgesic medication use in the first 72 hours following surgery completion (all opioids in IV morphine equivalents and total mg use of ibuprofen and/or acetaminophen combined).

Secondary outcome measures include mean PACU VAS (0-10) pain score, VAS pain score at 24, 48, and 72 hours post-surgery completion, nausea and emesis at 24, 48, and 72 hours post-surgery completion, urinary retention, and patient satisfaction with pain management at 72 hours and 7-10 days post op.

DESIGN

This is a prospective randomized, blinded, controlled clinical trial.

STUDY MEDICATION

Liposomal bupivacaine is being used per FDA indication (postsurgical analgesia) at an approved dose and route of administration (surgical site infiltration). It is also being given within the FDA labeled doses of the bupivacaine HCl given concomitantly, which recommends mg dose of bupivacaine HCl to liposomal not to exceed 1:2. Safety and efficacy of concomitant use has been prospectively studied (5). This study does not intend to pursue change to labeling or advertising. This study will be carried out in accordance with the applicable United States government regulations and Mayo Clinic research policies and procedures.

PARTICIPANTS

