- Patients in the control group will receive 0.25% bupivacaine HCl. 10cc will be injected bilaterally into each uterosacral ligament prior to the colpotomy incision. After entry into the posterior cul-de-sac, an additional 10cc will be injected bilaterally into the deeper uterosacral ligaments.

We plan to standardize preoperative medication, intraoperative anesthetic regimen, medication, administration in the recovery area, and discharge medication treatment (see appendix 1). Care will include key elements of a validated enhanced recovery protocol (6).

DATA COLLECTION

Demographic data including age, BMI, medical and surgical history, indication for surgery, and degree and type of pelvic organ prolapse will be collected.

Intraoperative fentanyl use will be recorded from the anesthesia record. Immediate postoperative opioid use will be retrieved from the EMR until discharge from PACU. Immediate nausea and emesis will be determined by total dose of antiemetics in PACU. Urinary retention will be determined as post void residual greater than 200 ml on catheterization or bladder scan. Patients will be offered PO opioid analgesics as first line therapy in PACU. Number and percentage of patients receiving intravenous opioids as second line therapy, thus failing PO as first line therapy in PACU will be recorded; however they will remain in the study.

Other intraoperative and immediate postoperative data will include completed procedure, surgery time, estimated blood loss, final pathology, and presence of failed voiding trial, length of stay in recovery, and numbers and reason for any unplanned admissions. Unplanned admission patients' data will be excluded and be recorded as a treatment failure.

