All patients will be discharged home with a diary to record analgesic use, VAS pain scores, and presence of nausea and emesis through 72 hours post-surgery (POD 3). Opioid use will be documented as total tablets of 5 mg oxycodone, hydromorphone 2mg, and non-opioid medication use as total tablets of acetaminophen 500 mg and/or ibuprofen 600 mg. VAS (0-10) pain scores will be logged at 6 hour intervals. Nausea and emesis will be documented as how many times patients felt nauseated, how many times they vomited, and total tablets of anti-emetic. Patients will be emailed twice a day with a link to record their documented scores. Those who prefer not to complete the surveys electronically will have the option to complete the paper questionnaire and diary. Those choosing the paper option will receive a daily phone call from study personnel blinded to study groups to remind them to complete their diary and questionnaire. Patient satisfaction for pain control will be assessed as a 0-10 scale question at the 72 hour mark and again at 7 to 10 days postop via telephone.

Allergic reaction to liposomal bupivacaine and local anesthesia toxicity will be assessed immediately on presentation to PACU, prior to discharge, and assessed by telephone and documented up to the 7 to 10th post-operative day. All doses of liposomal bupivacaine are within manufacturer labeling, and this is an FDA “on label” use of the drug (surgical site tissue infiltration). Concomitant bupivacaine HCl with liposomal bupivacaine doses are within manufacturer “on label” recommended ratio of 1:2. Intralipid 20% for local anesthetic toxicity treatment will be immediately available at all times prior to discharge. All data will be entered into HIPAA-compliant REDCap software.

SAMPLE SIZE

We plan to enroll and randomize 104 patients with the goal of obtaining complete data on at least 96 (47 per group) assuming a 10% loss to follow up. With a sample of 96, we achieve 80% power to detect a 30% difference in total opioid use at the 72 hour mark corresponding to an effect size of 0.6 at an alpha 0.05.

DATA ANALYSIS

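### IV acetaminophen given in PACU falls inside the 72-hour primary endpoint window, but the data items count only tablets, so the non-opioid total omits it

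*Combined protocol and SAP*

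**What the plan says.** The Objectives section sets the primary aim: to "compare total post-surgical analgesic medication use in the first 72 hours following surgery completion". The endpoint has an opioid part, in IV morphine equivalents, and a non-opioid part: "total mg use of ibuprofen and/or acetaminophen combined". Neither part is restricted by route or place of administration.

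Safety Monitoring keeps every patient in recovery for at least four hours. The PACU orders in Appendix I (Anesthesia Protocol, III. Recovery) begin: "First line: IV Tylenol, PO Oxycodone 5-10 mg or PO hydromorphone". They state no dose or number of doses for the IV acetaminophen.

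For PACU, the Data Collection section says: "Immediate postoperative opioid use will be retrieved from the EMR until discharge from PACU". The PACU list in Appendix I (Data Collection, section IV) has four items: opioids, antiemetics, pain scores and urinary retention. Non-opioid analgesics appear in two other places. The diary, which patients receive at discharge, records "non-opioid medication use as total tablets of acetaminophen 500 mg and/or ibuprofen 600 mg". Appendix I, section V, item b lists "Non-opioid medication use in total tablets of 600 mg ibuprofen and 500 mg acetaminophen".

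**The concern.** The endpoint definition and the items meant to supply it do not match. The definition runs from surgery completion and is in mg by any route. The collection items for non-opioids are in tablets, and an IV dose is not a tablet. No item collects IV acetaminophen, and no rule converts it to mg or tablet equivalents.

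This affects one of the two components of the primary endpoint, and the Data Analysis section names total non-opioid use as a group comparison. An analyst who follows the plan would report a total that starts, in effect, after the IV doses, while describing it as a total from surgery completion.

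**Working it through.** **Step 1. Trace each analgesic in the window to a data item.**

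| Use after surgery completion | In the endpoint? | Collected by |
|---|---|---|
| PACU opioids | Yes | EMR; Appendix I, IV.a |
| Home opioids | Yes | Diary; Appendix I, V.a |
| Home acetaminophen and ibuprofen tablets | Yes | Diary; Appendix I, V.b |
| PACU IV acetaminophen | Yes | No item |

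Oral acetaminophen given before surgery and ketorolac given during wound closure are not part of the gap: the first precedes the window, and the second is neither of the two named drugs.

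**Step 2. The plan's own figure.** The Sample Size section gives 47 per group for 80% power at effect size 0.6 and alpha 0.05, for total opioid use. Assuming a two-sided test, the t-test needs 44.6 per arm. Dividing by 0.955 for the Wilcoxon test gives 44.6 / 0.955 = 46.7, so 47 per arm, with power 80.3%. The 47 is reproduced. It rests on opioid use alone, so the missing acetaminophen does not change it.

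**Step 3. Scale of the omission for one patient.** The IV dose D is not in the documents. I assume a single dose and show D = 650 mg and D = 1000 mg; this is a scale for the calculation, not a view on dosing. With H the home total of both drugs, the missed share is D / (H + D).

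The discharge orders allow acetaminophen 1000 mg and ibuprofen 600 mg every 8 hours, so at most nine doses of each in three days:

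- 9 × 1000 = 9000 mg, 9 × 600 = 5400 mg, H = 14,400 mg
- 650 / 15,050 = 4.3%
- 1000 / 15,400 = 6.5%

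For an illustrative patient taking three doses of each at home:

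- 3 × 1000 = 3000 mg, 3 × 600 = 1800 mg, H = 4800 mg
- 650 / 5450 = 11.9%
- 1000 / 5800 = 17.2%

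**Step 4. Effect on the comparison.** If a proportion p of each arm receives one dose, the error in the difference of means is D × (p in control − p in study arm).

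| Difference in p between arms | D = 650 mg | D = 1000 mg |
|---|---|---|
| 0 | 0 mg | 0 mg |
| 10 points | 65 mg | 100 mg |
| 30 points | 195 mg | 300 mg |

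With equal use, both means are too low but their difference is right. The documents give no value for p in either arm.

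**The case against.** **The data list may not be exhaustive, and the EMR holds the dose anyway.** The Data Collection section names items that Appendix I lacks, such as blood loss and recovery length of stay, and section V of the appendix is not confined to home data, since its pain item includes PACU. IV acetaminophen is therefore probably recoverable. This stands, and it limits the harm. It does not close the gap: the non-opioid item is specified in tablets, and EMR retrieval of PACU analgesics is specified for opioids. Adding the dose only after looking at results would be a post hoc change to the primary endpoint.

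**A reader might infer that the omission shrinks the treatment difference toward zero**, because control patients in more pain would receive more PACU acetaminophen. The documents do not support a direction. The first-line order covers mild, moderate and severe pain alike, and escalation is to IV opioids, which are collected. The Data Collection section describes oral opioids as the first-line offer in PACU, so acetaminophen alone might go to patients with milder pain, which would point the other way.

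**A reader might also infer that the opioid total cannot be interpreted without the acetaminophen.** That goes too far. PACU opioids are recorded, allocation is randomized, recovery staff are blinded and both arms share the same PACU orders. The opioid comparison is valid under that common regimen.

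**Dividing by acetaminophen alone would make the omission look larger.** The endpoint combines the two drugs, so the combined total is the right denominator.

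**Conclusion.** The concern holds for the non-opioid component of the primary endpoint. As written, the plan leaves out IV acetaminophen given in PACU, so the reported total falls short of its own definition in any arm where the drug is used.

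Under the assumption of one 650 to 1000 mg dose, the shortfall for a patient who receives it is about 4 to 6.5% of the combined total at maximum home use and about 12 to 17% at the lower home use shown. If the share of patients dosed differs by 10 to 30 percentage points between arms, the mean difference is misstated by 65 to 300 mg. Repeat doses would increase these figures. Whether there is any between-arm bias, and in which direction, cannot be determined from the documents. The opioid total and the sample size stand.

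**What to change.** Add one item to Appendix I, Data Collection, section IV: acetaminophen and any ibuprofen given in PACU, by any route, in mg. Take it from the EMR record already used for PACU opioids. State that the 72-hour non-opioid total is PACU mg plus home tablets converted to mg (500 mg per acetaminophen tablet, 600 mg per ibuprofen tablet), with each dose counted once. Record this rule before any comparison by arm.

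The cost is one extra abstracted field. It adds no patient burden, does not change treatment and leaves the sample size as it is.
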